Furthermore, investigators should consider alternative treatment options, such as systemic therapies, at or after completing the Week 8 visit, if any participant meets all of the following criteria (Note: prior to initiation, the investigator should discontinue study cream and the therapy escalation will be recorded in the eCRF):

- IGA score ≥ 3
- EASI score ≥ 16
- Itch NRS score ≥ 4
- BSA $\geq 10\%$

During the VCE period, participants (including those in the escape arm) will have study visits every 4 weeks for up to 24 weeks total. At each of these visits, including Week 8, the participant's AD lesions will be evaluated by the investigator to determine whether the

participant requires continuation of treatment or should (re)enter an observation/no treatment period. If the IGA score is ≥ 1 , the participant will start or continue study cream BID. If the IGA score is 0 (clear), the participant will (re)enter an observation/no treatment period. Note: Participants should stop treatment application 3 days after the lesions have cleared.

Furthermore, during the VCE period (ie, starting at the Week 8 visit), participants will self-evaluate their AD symptoms between study visits and will treat areas of the skin (not to exceed 20% BSA) with active AD lesions only. If AD lesions clear at any time before the Week 24 visit, participants will stop treatment applications 3 days after the lesions have cleared and record the dates of these events in their eDiary. Participants who were in an observation/no treatment period will restart treatment at home at the first sign of recurrence and record the date of the new treatment. All treatment will be captured in the clinical database with the beginning and end dates as confirmed by the participant in the eDiary. A study staff representative or designee will contact the participant in between regularly scheduled clinic visits (eg, Weeks 10, 14, 18, and 22) to discuss eDiary compliance and to confirm the start and end date of treatment as applicable.

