If there are new areas to be treated, including expansion of existing areas or development of new areas, after consultation with the investigator, study cream should be applied to these areas in addition to the areas identified at the baseline visit (up to a maximum total of 20% BSA) for the remainder of the VC period, and the percentage of BSA to be treated will be recalculated and increased accordingly. This new estimate will be entered into the IRT system to calculate the number of tubes of study cream to be dispensed. During the VC period, participants whose additional new areas to be treated in addition to the areas identified at the baseline visit exceed 20% BSA will be discontinued from study treatment and complete the ET visit.

The VCE period starts at the Week 8 visit and completes at the Week 24 visit, with the final possible application being the evening application on the day before the Week 24 visit. During the VCE period, only areas with active disease should be treated.

After completing 8 weeks of continuous treatment, all eligible participants with an adequate response, defined as achieving at least EASI50 from baseline, will continue their blinded treatment allocation and will be evaluated during an additional 16-week VCE period for durability of response. Participants will be eligible to enter the ruxolitinib 1.5% cream open-label escape arm if EASI50 is not achieved at Week 8 or if an EASI50 response from baseline is lost during the VCE period. (Note: < EASI50 must be observed at 2 consecutive visits, one of which can be an unscheduled visit, at least 1 week apart.)

The start and end dates of treatment applications will be captured by the participant. Once the lesions clear (IGA score of 0), participants should continue to apply study cream for an additional 3 days to the areas of the body where lesions were last present before discontinuing treatment. Following clearance, if a lesion recurs, treatment should be resumed at the first sign of recurrence.

At any time during the VCE period, if a participant's total AD-affected area exceeds 20% BSA, the participant will be discontinued from study treatment and complete the ET visit.

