6.1.1. Study Treatment Application Guidance

Participants should remove study cream from the tube and apply the study cream with their fingertip (see [Figure 2](#)) in small amounts until all of the areas to be treated are covered by a thin, even film. Additional training will be provided in the SRM.

Figure 2: Study Cream Application Using a Fingertip

Source: DermNet New Zealand (www.dermnetnz.org).

In the clinic, the amount of study cream used will be determined by weighing a tube before and after the participant applies a thin film of study cream to the affected areas. New tubes of study cream will be provided at each visit.

Study cream should be applied in front of site staff for all on-site visits. The Day 1 baseline visit should be performed in the morning (AM). The study personnel need to ensure that they understand the quantity to be used and the application method. For all other (non-Day 1) visits, the participant should apply either of the 2 daily doses at the site, as long as the previous dose was applied at least 4 hours prior (see Section 8.4).

Study cream application does not apply to the Week 8 visit if the IGA score is 0 or to the Week 24 or ET visits.

Application instructions will be provided by the site study staff, and the participants will record their daily applications plus any missed or interrupted doses via an eDiary. Participants must not apply study cream more or less often than BID. Refer to the SRM for participant instructions for handling study cream.

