10.2. Populations for Analysis

The populations for analysis are provided in [Table 10](#).

Table 10: Populations for Analysis

Population	Description
ITT	The ITT population includes all randomized participants. Treatment groups for this population will be defined according to the treatment assigned at randomization.
PP	
The PP population includes randomized participants who are considered to be sufficiently compliant with the Protocol. In general, the following are important Protocol deviations that may significantly affect the primary analysis:
 
 • Missing data for any of the coprimary endpoints. • Overall application compliance less than 80% during the VC period. 
Participants with 1 or more such deviations will be excluded from the PP population. In addition, important Protocol deviations related to inclusion/exclusion criteria, discontinuation criteria, and use of prohibited concomitant medications will be reviewed. Decisions as to whether any of these deviations warrant exclusion from the PP population will be made prior to unblinding.

VCE primary	The VCE primary population includes all participants who entered the VCE period and applied study cream at least once during the VCE period. Participants will be analyzed according to the treatment assigned at randomization. For participants who enter the escape arm, only information prior to entry to the escape arm will be presented.
VCE escape	The VCE escape population includes all participants in the VCE primary population who moved to the ruxolitinib 1.5% cream BID open-label escape arm.
Safety	The safety population includes all participants who applied study cream at least once. Treatment groups for this population will be determined according to the actual treatment the participant applied on Day 1.
PK-evaluable	The PK-evaluable population includes participants who applied ruxolitinib 1.5% cream at least once and provided at least 1 postbaseline blood sample for PK analysis. The study pharmacokineticist will review data listings of participant administration and sample records to identify participants to be excluded from the analysis.

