### **5.3.5. Vehicle-Controlled Extension Primary Population**

The VCE primary population includes all participants who entered the VCE period and applied study cream at least once during the VCE DB period. Participants will be analyzed according to the treatment assigned at randomization. For participants who enter the escape arm, only information prior to entry to the escape arm will be presented.

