### **5.3.7. Vehicle-Controlled Extension Re-Treatment Evaluable Population**

The VCE re-treatment evaluable population includes all participants who entered the VCE DB period.

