#### **7.5.2.4. Analysis of Desensitization and Rebound in the VCE DB Period**

The following categorical parameters will be summarized by treatment to assess rebound upon treatment cessation:

- Proportion of participants who experience a relapse after study treatment discontinuation. (ie, proportion of participants among EASI75 responders who are on study treatment at Week 24 who meet relapse criteria [loss of EASI50 from baseline] at the safety follow-up visit)

[figure not shown]
The following endpoints will be summarized by treatment and visit to assess desensitization upon treatment cessation:

[figure not shown]
[figure not shown]
- Proportion of time off study treatment due to lesion clearance during the VCE period by visit
- Proportion of time on study treatment during the VCE period by visit

Time to first re-treatment is defined as the interval between the first interruption due to lesion clearance starting from Week 8 to the end of the VCE period and the time of starting the re-treatment. This analysis will be performed in the VCE re-treatment evaluable population as defined in Section 5.3.7. The Kaplan-Meier estimate of median time to first re-treatment will be presented with its 95% CI. The 95% CI will be calculated using the method by Brookmeyer and Crowley (1982).

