2.9.1	Summary and Analysis of By-Visit EQ-5D-5L VAS Score in the DB Treatment Period	ITT	
2.9.3	Summary of Participants in Each Category of EQ-5D-5L Score in the DB Treatment Period	ITT	

Table No.	Title	Population	Standard
WPAI-AD			
2.10.1	Summary and Analysis of By-Visit WPAI-AD Score in the DB Treatment Period	ITT	
PROMIS			
2.11.1	Summary and Analysis of By-Visit PROMIS Short Form- Sleep-Related Impairment 8a Score in the DB Treatment Period	ITT	
2.11.3	Summary and Analysis of By-Visit PROMIS Short Form- Sleep Disturbance 8b Score in the DB Treatment Period	ITT	
HADS			
2.12.1	Summary and Analysis of By-Visit HADS Score in the DB Treatment Period	ITT	
BSA			
2.13.1	Summary and Analysis of Total %BSA Affected by AD in the DB Treatment Period	ITT	
2.13.3	Summary of By-Visit Change From Baseline in the Number of Intertriginous Regions With Active AD Involvement in the DB Treatment Period	ITT	
Desensitization and Rebound in the VCE DB Period			
2.14.1	Summary and Analysis of Participants Experiencing a Relapse After Study Treatment Discontinuation	Study completers who achieved EASI75 at Week 24 and entered safety follow-up	
2.14.2	Summary and Analysis of Participants' By-Visit Time Off Study Treatment Due to Lesion Clearance During VCE Period	VCE Primary	
2.14.3	Summary and Analysis of Participants' By-Visit Time on Study Treatment During the VCE Period	VCE Primary	
2.14.4	Summary and Analysis of Time to First Re-Treatment During the VCE Period	VCE Re-Treatment evaluable	
Safety			
Exposure			
3.1.1.X	Summary of Exposure During the VC Period	Safety	X
3.1.2	Summary of Exposure (Baseline to Week 24)	Safety	X
3.1.3	Summary of Study Drug Compliance During the VC Period	Safety	X
Adverse Events			
3.2.1.1.X	Overall Summary of Treatment-Emergent Adverse Events in the VC Period	Safety	X
3.2.1.2	Overall Summary of Treatment-Emergent Adverse Events for Participants Who Applied Ruxolitinib Cream Throughout the Study (Baseline to Week 24)	Safety	X
3.2.1.3	Overall Summary of Exposure-Adjusted Treatment-Emergent Adverse Events (Baseline to Week 24)	Safety	X
3.2.2.1.X	Summary of Treatment-Emergent Adverse Events by MedDRA System Organ Class and Preferred Term in the VC Period	Safety	X
3.2.2.2	Summary of Treatment-Emergent Adverse Events by MedDRA System Organ Class and Preferred Term for Participants Who Applied Ruxolitinib Cream Throughout the Study (Baseline to Week 24)	Safety	X

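### The VCE time-on/off tables can drop participants who stay clear without cream, and time to first re-treatment has no start date for participants who never clear

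*SAP*

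**What the plan says.** **The population.** SAP 5.3.5: "The VCE primary population includes all participants who entered the VCE period and applied study cream at least once during the VCE DB period". Protocol Table 10 (Section 10.2) sets the same condition: "The VCE primary population includes all participants who entered the VCE period and applied study cream at least once during the VCE period".

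**Where it is used.** SAP Appendix A assigns VCE primary to Table 2.14.2, whose title includes "By-Visit Time Off Study Treatment Due to Lesion Clearance During VCE Period", and to its companion on time on treatment, Table 2.14.3. It also assigns it to extension itch (2.3.5.2), extension skin pain (2.6.1.2) and extension disposition (1.1.2.2). The SAP body text differs. Section 5.3.1 gives ITT as the set for efficacy in both blinded periods, and Section 6.2 describes extension disposition for those who entered the VCE period, with no application condition.

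**What a clear participant does.** Protocol 4.1, for visits from Week 8 on: "If the IGA score is 0 (clear), the participant will (re)enter an observation/no treatment period". SAP Section 3 repeats this. Protocol 6.1.1 adds: "Study cream application does not apply to the Week 8 visit if the IGA score is 0". Protocol 6.1, however, says: "Once the lesions clear (IGA score of 0), participants should continue to apply study cream for an additional 3 days". A note in Protocol 4.1, directly after the observation rule, also places the stop 3 days after clearance.

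**Re-treatment.** SAP 7.5.2.4: "Time to first re-treatment is defined as the interval between the first interruption due to lesion clearance starting from Week 8", running to the start of re-treatment. The analysis set is that of SAP 5.3.7: "The VCE re-treatment evaluable population includes all participants who entered the VCE DB period".

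**The concern.** The extension exists to describe durability under as-needed use, and staying clear without cream is its best outcome. The at-least-one-application condition can remove exactly those participants from the endpoint that measures time off cream. Sustained clearance is foreseen: Protocol 4.1 and 8.9.1 have a special visit rule for participants in observation with IGA 0 from Week 20 or earlier through Week 24. If clearance differs by arm, so does the exclusion, and the between-arm contrast shrinks.

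The re-treatment endpoint has the opposite mismatch. Its population is wider than the group in which the interval exists. A participant who never stops for clearance has no time origin, and the definition paragraph gives no handling or censoring rule. The programmer must choose one, and one of the available choices distorts the curve.

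The two sets also disagree. A participant clear from Week 8 onward counts in Table 2.14.4 (re-treatment) but may be absent from Tables 2.14.2 and 2.14.3.

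**Working it through.** No sample size, power or alpha figure in the plan depends on this, so there is no stated figure to reproduce.

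**1. Who is excluded.** Membership of VCE primary follows from the passages set side by side:

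| Step | Source | Consequence |
|---|---|---|
| No clearance-related stop before the extension | Protocol 6.5 | Off-treatment time can start only at Week 8 |
| IGA 0 at Week 8 leads to observation | Protocol 4.1; SAP 3 | No cream prescribed |
| No on-site dose at Week 8 if IGA is 0 | Protocol 6.1.1 | No application at the visit |
| Lesions never return | Participant's course | No later application; excluded |
| Cream for 3 more days after clearance | Protocol 6.1; note in 4.1 | If done after Week 8, at least one application; included |

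The first four rows exclude the participant and the last row includes the same participant. The text does not say which applies to someone found clear at Week 8. A participant with IGA 1 continues cream and is not affected.

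**2. Size for time off.** Let s be the share of entrants excluded and m the mean time off among the rest. Both are assumptions; the documents give neither.

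- All entrants: s × 100% + (1 − s) × m. VCE primary reports m. Shortfall: s × (1 − m).
- s = 5%, m = 50%: all entrants 52.5%, reported 50%, shortfall 0.05 × 0.50 = 2.5 points.
- s = 20%, m = 30%: all entrants 44%, reported 30%, shortfall 0.20 × 0.70 = 14 points.
- Wider ranges (s = 5-30%, m = 20-40%): from 0.05 × 0.60 = 3 points to 0.30 × 0.80 = 24 points.
- s = 0, because all apply the 3-day continuation after Week 8: shortfall 0.

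Between arms, assume s = 20% and m = 40% on ruxolitinib, and s = 5% and m = 20% on vehicle. Means among all entrants are 0.20 + 0.80 × 0.40 = 52% and 0.05 + 0.95 × 0.20 = 24%, a difference of 28 points. VCE primary shows 40% − 20% = 20 points.

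**3. Time to first re-treatment.** Let u be the share who never clear. Assume exponential re-treatment with a 4-week median among those who clear, so λ = ln 2 / 4.

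- Never-cleared participants left out or censored at time 0: the curve is unchanged at 4 weeks, but the reported N is not the risk set.
- Never-cleared participants carried as event-free: S(t) = u + (1 − u)exp(−λt), with median −ln[(0.5 − u)/(1 − u)]/λ.

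| u | Apparent median (weeks) |
|---|---|
| 0 | 4.0 |
| 10% | 4.7 |
| 20% | 5.7 |
| 30% | 7.2 |
| 40% | 10.3 |
| 50% or more | not reached |

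Under that choice, the arm that clears least appears to go longest without re-treatment.

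**The case against.** The strongest reply concerns the 3-day continuation. If everyone found clear at Week 8 applies cream for 3 further days, each meets the at-least-once condition and the exclusion disappears altogether. This stands as a limit. A reader might infer that all participants clear at Week 8 are lost from VCE primary, and the documents do not support that. Exclusion needs IGA exactly 0 at Week 8, no continuation after the visit and no later application. What remains is that set membership turns on passages that conflict.

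Second, SAP 5.3.1 and 6.2 already point to ITT or to entrants, most extension efficacy tables (IGA, EASI, SCORAD, DLQI, POEM, BSA) use ITT, and Appendix A calls its list a guideline. This narrows the scope and shows that body text and table list disagree. It does not say which set the time-on/off tables will use.

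Third, a reader might infer that re-treatment times will be biased. The SAP does not say never-cleared participants will be carried as event-free. Doing so from Week 8 would contradict the stated time origin, and only Kaplan-Meier medians with confidence intervals are planned. Parts of SAP 7.5.2.4 are also not reproduced in the public text. The supportable point is an undefined origin and no handling rule in the definition paragraph.

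Fourth, deleting the application condition from VCE primary would do harm. That set also serves extension exposure and safety (SAP 6.4, 9.1 and the note under the Appendix A tables), where the condition is ordinary. Unexposed participants would enter the adverse event denominators with no defined treatment duration. This is correct, and the fix avoids it.

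Finally, limiting the re-treatment set to those who cleared conditions on a post-randomisation event. That is also correct. The endpoint exists only in that group, so the result must be labelled descriptive.

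**Conclusion.** The concern holds in limited form. As written, Tables 2.14.2 and 2.14.3 can omit participants with 100% time off, and time to first re-treatment is assigned to participants for whom it is undefined.

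The size of the first problem is unknown. The 2.5-14 point shortfall rests on an assumed 5-20% excluded and 30-50% mean time off in the rest, and the true value may be zero. That the shortfall is larger on ruxolitinib is likely only if that arm clears more; if so, the effect is to understate its benefit. The second problem distorts the estimate only if never-cleared participants are carried as event-free.

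A reader might infer a threat to the trial's main conclusions. There is none. These are secondary endpoints outside the fixed testing sequence, and the coprimary and key secondary results, power and alpha do not depend on them. Severity: moderate.

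**What to change.** 1. Keep VCE primary as defined for extension safety and exposure.
2. Use all participants who entered the VCE DB period for Tables 2.14.2, 2.14.3, 2.3.5.2, 2.6.1.2 and 1.1.2.2. Count a participant who never re-applies as 100% off and 0% on. Align Appendix A with SAP 5.3.1 and 6.2, or state the exceptions there.
3. Define the re-treatment evaluable population as VCE DB entrants with at least one documented stop for lesion clearance. Start the clock at that stop and censor at escape, discontinuation or Week 24. Report by arm the proportion who ever clear, and state that the set is conditioned on a post-randomisation event and is descriptive.
4. Reconcile the passages on direct entry to observation (Protocol 4.1, 6.1.1; SAP 3) with those on 3-day continuation (Protocol 4.1, 6.1), since population membership depends on them.
5. List the changes in SAP 11.1, which at present mentions only clearer wording for the VCE primary and escape populations.

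**Cost.** SAP wording and two derived flags, using start and stop dates the eDiary already collects. VCE primary still matches Protocol Table 10. The re-treatment set becomes smaller, and extension efficacy and safety tables may show different denominators. The changes should be made before the primary database lock, because the sponsor is unblinded after it (Protocol 10.6).

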### **5.3.6. Vehicle-Controlled Extension Escape Population**

The VCE escape population includes all participants who moved to the ruxolitinib 1.5% cream BID open-label escape arm. All efficacy and safety analyses for the escape arm will be conducted with the VCE escape population.

### **5.3.7. Vehicle-Controlled Extension Re-Treatment Evaluable Population**

The VCE re-treatment evaluable population includes all participants who entered the VCE DB period.

## **6. BASELINE, EXPOSURE, AND DISPOSITION VARIABLES AND ANALYSES**

[Appendix A](#) provides a list of planned tables, figures, and listings. Sample data displays are included in a separate document.

### **6.1. Baseline and Demographics, Physical Characteristics, and Disease History**

#### **6.1.1. Demographics**

The following demographics will be summarized for the ITT population, the VCE primary population, and the VCE escape population: age, age group, sex, race, ethnicity, weight, height, and body mass index.

#### **6.1.2. Baseline Disease Characteristics**

Baseline disease characteristics summarized for the ITT population, the VCE primary population, and the VCE escape population include but are not limited to the following:

- Time since first onset of AD
- Prior history of asthma (no/yes)
- Prior allergies (food, environmental) (no/yes)
- History of contact dermatitis (no/yes)
- Common complications of AD
- Time since onset of current AD episode
- Facial and/or neck involvement (no/yes) during past episodes
- Number of AD episodes/flare-ups over the last 12 months
- Average duration of episodes/flare-ups over the last 12 months
- Baseline EASI score
- Baseline %BSA
- Baseline DLQI score
- Baseline Itch NRS score

- Baseline Skin Pain NRS score
- Inadequate response to TCS (no/yes)
- If inadequate response to TCS is no, prior systemic therapy over the last 12 months (no/yes)
- If inadequate response to TCS is no, prior phototherapy over the last 12 months (no/yes)
- Intolerance to TCS (no/yes)
- Contraindication to TCS (no/yes)
- Inadequate response to TCI (no/yes); if inadequate response to TCI is no, prior systemic therapy over the last 12 months (no/yes)
- If inadequate response to TCI is no, prior phototherapy over the last 12 months (no/yes)
- Intolerance to TCI (no/yes)
- Contraindication to TCI (no/yes)
- Prior systemic therapy (no/yes) over the last 12 months
- Prior phototherapy (no/yes) over the last 12 months
- Intertriginous involvement at baseline (no/yes)

